Together, these data support our *overarching hypothesis*: that with the same volume of exercise, **HIIT will lead to better physical function and reduced patient-reported fatigue through improvements in mitochondrial bioenergetics compared with CME among older PWH**. We further hypothesize that older PWH randomized to HIIT will maintain self-directed exercise better than those in CME when exercise is no longer supervised, and that behavioral support will help to maintain adherence. Through a three-site (Seattle, WA, Aurora, CO, and Birmingham, AL), clinical trial comparing the clinical and bioenergetic effects of two exercise regimens that vary by interval and intensity (HIIT or CME), we will test our hypotheses through the following aims:

**AIM 1.** Compare the effects of two exercise regimens varying by interval and intensity on *primarily* physical function performance (i.e., 400-m walk time) and *secondarily* on patient-reported fatigue at 16-weeks. We **hypothesize** that PWH randomized to HIIT will experience greater improvements in physical function and reductions in fatigue compared

to CME. **Approach:** We will randomize 180 PWH (aged 50-80 years) into one of two supervised 16-week exercise interventions and compare changes in physical function and patient-reported fatigue over time.

**AIM 2.** Evaluate bioenergetic mechanisms underlying HIIT and CME. We **hypothesize** that PWH randomized to HIIT will have improved mitochondrial bioenergetics (i.e., mitochondrial respiration rate and ETC activity). **Approach:** We will evaluate 16-week changes in skeletal muscle and systemic (peripheral blood mononuclear cells [PBMCs]) mitochondrial activity among PWH in response to supervised exercise.

**AIM 3.** Describe and compare the effect of a biobehavioral coaching intervention to enhance self-directed exercise. **Approach:** After 16 weeks of supervised exercise, HIIT and CME participants will be randomized (in a factorial design) to a 12-week coaching intervention (vs. control) using tailored text messages to support exercise adherence. Physical activity amount (via accelerometry) and experience (via interviews) will be compared between arms using mixed analytic methods.

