#### **Procedures/Outcome Measures:**

**Randomization.** After the conclusion of the exercise intervention, participants will be randomized 1:1 (with even allocation of HIIT vs CME) to receive the coaching or control intervention (details below).

**Quantitative Measures.** PA will be measured with a widely-used and validated measure, the ActiGraph accelerometer (ActiGraph, LLC, Fort Walton Beach, FL), as described in Aim 1. **Primary exercise endpoints** are (1) time spent in moderate-to-vigorous PA (MVPA), and (2) steps per day.

These endpoints will be set with the adult cut-points for tri-axial accelerometers. All participants will complete a daily log during the maintenance phase to track aerobic and resistance exercise. This log will include the time, type, duration, and setting of exercise completed each day. It will be triangulated with the accelerometry data and reported descriptively.

**Qualitative Measures.** **One-on-one Interviews (this will be optional).** First, we will pilot test an interview guide on 2-3 PWH at UW and UCD-AMC and revise it accordingly. A final guide will be used to direct subsequent interviews consistently at both sites. The interviews will take place in a secure, private location. Questions will address the participants' perceptions of exercise; experiences with HIIT, CME, or resistance training; the coaching intervention; and what they think will help them sustain PA over the long-term (Fig. 4). If a participant withdraws from the study, he/she may be offered a withdrawal interview to explore reasons for withdrawal and/or ways to improve the study intervention. Interviews will take ~ 30 minutes, be audio-recorded, and transcribed verbatim. [name] has over 15 years of experience designing, implementing, and analyzing data from qualitative studies and has successfully trained and managed qualitative data collectors across sites, obtaining high-quality data.

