## E. Potential Scientific Problems:

We considered giving all participants the text messaging intervention and evaluating it using a quasi-experimental pre-post design. However, given that there are few evidence-based strategies to support long-term, self-directed exercise, we decided to test this effect using the most rigorous design available- a randomized clinical trial. This will allow us to assess causality and enable us to make clinical recommendations at the conclusion of this study. Although initially concerned about requiring older PWH to have cellphones, our recent work found that 85% of PWH have a cell phone (mean age 52 years) and that all send texts daily. These data, coupled with data from co-I [name] indicating equally high use of cell phone and texts at UCD-AMC, suggest minimal impact of this criterion. Further, use of this coaching intervention is congruent with the recent NIH initiative (PA18-347) to stimulate biobehavioral and technological interventions to improve the health of vulnerable populations. Fasted samples will be banked at weeks 0 and 16 for future analyses, including assessment of inflammatory markers, myokines, metabolomics, proteomics, or transcriptomics, pending our initial analyses and the state of the science.

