## F. Data Analysis Plan:

**Statistical Considerations.** We hypothesize that among older PWH, HIIT will lead to better physical function and reduced fatigue through improvements in mitochondrial bioenergetics compared with CME.

**Sample Size Calculations:** We assume a 1:1 randomization to HIIT or CME balanced by site, sex ( $\geq 25\%$  women) and age category (50-59, 60-69, and 70+) with a conservative 20% dropout rate, resulting in 40 evaluable participants/group. The second randomization at week 16 and will also be balanced by initial randomization (2x2 factorial design). Aim 1 and 2 power calculations assume two-sided, 2-sample/paired *t*-tests for between/within group comparisons of the change from baseline with a 0.05 significance level. We assume conservative within subject correlations ( $\rho$ ) of 0.7 or 0.5 to estimate the standard deviation (SD) of the outcome change, larger correlations and repeated measures will result in additional power. The Aim 1 primary outcome is change in 400-MWT. We assume an effect size comparable to Toohey, an intervention comparing HIIT to CME among middle-aged (mean age 51, SD 12 years) cancer survivors that resulted in a mean (SD) difference of 97 (82) and 36 (68) meters in 6-minute walk distance among HIIT and CME, respectively. Using  $\rho=0.7$ , and a sample size of 40/group, we will have  $>88\%$  power to detect a comparable *between* group differences of 45 (38) and 20 (38) second improvement in 400-MWT in HIIT and CME, respectively. For reference, in our prior exercise study, PWH had a 25 second improvement in 400-MWT. This also provides  $>99\%$  and  $>81\%$  power to detect *within* group differences in the HIIT and CME arms. For morning and evening fatigue, we assume a baseline mean of 19(8) and 27(8) points, respectively ([name], unpublished data). With  $\rho=0.5$ , and a sample size of 40/group, we will have  $>80\%$  to detect a change of  $\geq 27\%$  and  $\geq 20\%$ , respectively. The primary Aim 2 outcome is change in State 3 respiration. Based on Robinson, we estimate a baseline mean (SD) of 580 (180) pmol  $O_2$ /min/mL using  $\rho=0.5$ . This provides  $>81\%$  power to detect a difference in the change of 50% (HIIT) and 30% (CME). The muscle substudy is considered exploratory, however, we anticipate adequate power. Using preliminary data, combining HEALTH+ exercise groups (N=24), provides  $>80\%$  power to detect a change of -8.7% in MRI-PDFF of HEALTH+ participants. For within exercise group (CME or HIIT) comparisons, a sample size of 12 provides  $>80\%$  power to detect a difference of -12.5%. For the CME versus HIIT change from baseline comparison, a sample size of 12 per group provides  $>80\%$  power to detect group differences of 9.8%. For the change in OxPhos, combining HEALTH+ exercise groups (N=24, 3 dropouts/group), provides  $>80\%$  power to detect an OxPhos change of 0.039. For within exercise group (CME or HIIT) comparisons, a sample size of 12 provides  $>80\%$  power to detect an OxPhos difference of 0.055. For the CME versus HIIT change from baseline comparison, a sample size of 12 per group provides  $>80\%$  power to detect group OxPhos differences of 0.056. For the change in aim 3, combining HEALTH+ exercise groups, a sample size of N=24 (3 dropouts/ group), provides  $>80\%$  power to detect a 21%  $\dot{V}O_2$  change in HEALTH+ participants. For within exercise group (CME or HIIT) comparisons, a sample size of 12 provides  $>80\%$  power to detect 33% change in  $\dot{V}O_2$ . For the CME versus HIIT change from baseline comparison, a sample size of 12 per group provides  $>80\%$  power to detect a 30% difference in the 16-week change from baseline.

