**Aim 3:** Quantitative data will be summarized and used to describe physical activity (PA) amount and mode and then categorize the sample (see below for synthesis of data). After redacting identifying information, verbatim transcriptions of interviews will be entered into Dedoose, a secure, cloud-based qualitative analysis program. Our quality assurance protocol will include checking 25% of the transcripts to verify accuracy of the transcriptions and double-coding 10% of the transcripts to ensure inter-coder reliability of 80% or greater. Under MPI [name]'s direction, all responses will be analyzed using standard qualitative analytic techniques: identification of themes; coding of participants' responses by these themes performed independently by two team members (who have graduate-level training in qualitative coding); resolution of any coding discrepancies will be done by a third team member. To ensure consistency, a codebook will be developed to create universal definitions for each code. The codebook will contain all codes, their definition, and exemplar quotes and will be iteratively tested until all coders agree it captures the breadth and depth of the perceptions about HIIT, CME, the coaching intervention, and sustaining long-term PA in PWH. We will search for *a priori* codes that describe the perceptions of HIIT and CME and long-term PA maintenance based initially on our literature review. Significant inductive (emerging) codes will also be identified. Coded items will be grouped together into distinct themes. Group analysis meetings will be held to compare independently-developed codes for similarity and further direction. This data reduction method, encompassing a team-based analysis, creates a robust iterative process through which the data are thoroughly discussed and analytical consensus achieved.

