**Synthesis of quantitative and qualitative methods:** The goal of the Aim 3 mixed-methods analysis to fully describe and compare the perceptions of HIIT, CME, and effect of the coaching intervention to enhance self-directed PA in PWH. Our synthesis will use the qualitative data from 40 PWH to confirm quantitative findings and provide depth to our comparisons between HIIT vs CME (and coaching vs control) groups, and ultimately to identify factors that will enhance targeted interventions to help sustain long-term, self-directed PA in this population. To accomplish this, we will apply quantitative qualifiers to qualitative data to help fully understand the data. We will quantitatively categorize those in the HIIT and CME group, by sex, and self-directed exercise habit. We will visually depict these data using tools available in Dedoose and create a summary table with the following columns organized by coaching vs control and HIIT vs CME groups: Participants whose exercise (a) was maintained at 28 weeks, (b) declined after the supervised intervention but who still exercised, (c) stopped 16 weeks, with the following rows: (i) perceptions supporting exercise habits, (ii) perceptions of challenges to developing exercise habits, (iii) data explaining how the interventions affected exercise habits, and (iv) additional themes or patterns that emerge inductively from the data.

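### Aim 3 re-randomises participants to test coaching against control, but specifies no model, contrast or interval for that comparison on MVPA and steps over weeks 17-28

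*Combined protocol and SAP*

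**What the plan says.** **Design.** The Randomization paragraph of Aim 3 says that "participants will be randomized 1:1 (with even allocation of HIIT vs CME) to receive the coaching or control intervention". Sample Size Calculations adds: "The second randomization at week 16 and will also be balanced by initial randomization (2x2 factorial design". The Aim 3 Quantitative Measures paragraph lists two primary exercise endpoints: "1) time spent in moderate-to-vigorous PA (MVPA), and (2) steps per day". Secondary Outcome Measures, item 6, places actigraphy activity time and daily step count in weeks 17-28.

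**Purpose.** Section E explains that a pre-post evaluation of the text messages was considered and set aside: "we decided to test this effect using the most rigorous design available- a randomized clinical trial". It gives causal assessment and clinical recommendations as the reason. The Specific Aims state that "Physical activity amount (via accelerometry) and experience (via interviews) will be compared between arms using mixed analytic methods".

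**Analysis.** Under Aim 3 in the Analysis Plan, the quantitative part is a single sentence: "Quantitative data will be summarized and used to describe physical activity (PA) amount and mode and then categorize the sample". The rest of that paragraph concerns interview coding. The synthesis paragraph that follows says "Our synthesis will use the qualitative data from 40 PWH to confirm quantitative findings". It then describes a summary table by arm with three exercise categories (maintained, declined, stopped), whose rows are perceptions and themes.

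**Sizing.** In Sample Size Calculations, "Aim 1 and 2 power calculations assume two-sided, 2-sample/paired" t-tests. Nothing is said there about power for Aim 3.

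**The concern.** A randomised comparison that is meant to support a causal statement needs a stated effect measure, analysis set, time window, covariates and handling of the factorial structure. The Aim 3 text gives none of these. Summarising activity and sorting people into three categories does not by itself produce an estimate of the coaching effect with its uncertainty.

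If the plan is followed as written, the coaching conclusion on weeks 17-28 activity would rest on description. If an inferential analysis is added later, these choices could be made after the data are seen: endpoint, time point, adjustment, interaction and treatment of invalid wear. The same applies to the hypothesis in the Specific Aims that HIIT participants will maintain exercise better than CME participants.

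**Working it through.** **Step 1. Does any other section supply the contrast?** The sections that could do so are set against what is needed: coaching versus control, on MVPA and steps, over weeks 17-28.

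| Section | What it gives | Why it does not fill the gap |
|---|---|---|
| Analysis Plan, Aims 1 and 2 | Linear mixed model of change from week 0 | Headed Aims 1 and 2; no coaching term |
| Missing Data | Mentions mixed models for repeatedly measured outcomes, with multiple imputation as sensitivity analysis | General text; no outcome, contrast or coaching term |
| Exploratory Outcome Measures, item 10 | Activity adherence in weeks 17-28 by exercise and coaching arm | Names an outcome, no method |
| Synthesis paragraph | Refers to comparisons between groups | Describes a table, no model or interval |
| Cognitive Substudy, stage 2 model | Full factorial model with coaching, exercise arm and time | Outcome is cognitive score |
| Cognitive Substudy, secondary aim and EMA models | Coaching as a predictor of physical activity, and mediation with total effects and intervals | Physical activity at 12 months, in a substudy that is optional at two sites |

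None of them gives the week 17-28 coaching contrast.

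**Step 2. What could the contrast detect?** The plan has no Aim 3 figure to reproduce, so this step only illustrates size. Assumptions: two-sided alpha 0.05 and 80% power (alpha is stated for Aims 1 and 2 only), two equal coaching arms pooled over HIIT and CME, no covariate adjustment.

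Number per coaching arm, from the documents:
- 40: Sample Size Calculations states 40 evaluable per exercise group, so 80 in total; 80 / 2 = 40.
- 50: the Study Measures by Site table marks actigraphy for UW/UCD and not for UAB. The enrolment table expects 50 completers at each of those two sites; (50 + 50) / 2 = 50.
- 72: the Aim 3 Participants paragraph has up to 180 completing accelerometry. With the stated 20% dropout, 180 x 0.8 / 2 = 72.

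Formula (normal approximation): d = (1.960 + 0.842) x sqrt(2/n), in SD units.
- n = 40: 2.802 x 0.2236 = 0.63 (t-test 0.634)
- n = 50: 2.802 x 0.2000 = 0.56 (t-test 0.566)
- n = 72: 2.802 x 0.1667 = 0.47 (t-test 0.470)

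For an assumed true effect of 0.5 SD, t-test power is 60%, 70% and 85%. If the week-16 value is a covariate with an assumed correlation of 0.5, the residual SD is sqrt(1 - 0.25) = 0.866 of the raw SD, and power becomes 72%, 82% and 93%.

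The documents give no SD for MVPA or steps, so these figures cannot be turned into minutes or step counts.

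**The case against.** The strongest reply is that the plan does intend a comparison. The Specific Aims, exploratory outcome 10, Section E and the synthesis paragraph all say so. That stands: a reader might infer that the coaching contrast will never be tested, and the documents do not support that. They support only that no method for testing or estimating it is specified.

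A reader might also infer that the second randomisation goes unused. It does not. The cognitive stage 2 model uses the coaching assignment, and so do the substudy's 12-month activity models. In the latter, each predictor is first fitted separately, so a coaching association with activity is estimated before any screening on significance. These analyses concern a different outcome, or a different time point and a subset.

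Nor do the documents confine the accelerometry comparison to the 40 interviewees, or leave the interviews with nothing to confirm: arm-level summaries are quantitative findings, though without an estimated effect.

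Finally, Aim 3 is titled as describing as well as comparing, and its activity measure is a secondary outcome of the trial. That limits the consequence. It does not reconcile a descriptive method with the causal purpose given in Section E.

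**Conclusion.** The point holds as a gap in specification. The plan randomises to coaching in order to assess causality and says arms will be compared, yet for MVPA and steps over weeks 17-28 it specifies only summary, description and categorisation. It should be corrected before the Aim 3 data are analysed. The trial's primary conclusion does not depend on it.

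The detectable coaching difference lies between about 0.47 SD (72 per arm) and 0.63 SD (40 per arm), with 0.57 SD if only the two sites marked for actigraphy contribute. These values rest on an assumed alpha and power and an unadjusted two-arm comparison. The 0.5 SD effect and the 0.5 correlation used for the power figures are also assumptions. The larger sample should not be taken for granted while the site table and the Aim 3 Participants paragraph disagree.

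**What to change.** In the Aim 3 paragraph of the Analysis Plan:

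1. **Main analysis.** Fit a linear mixed model to MVPA, and another to steps per day, at the maintenance accelerometry visits. Include everyone re-randomised, as randomised. Fixed effects: coaching, exercise arm, visit, coaching-by-visit, week-16 value of the outcome, site, sex and age category.
2. **Estimate.** Report coaching minus control with 95% CI over the week 17-28 period that the outcome list defines, averaged over HIIT and CME. Give week 28 as a supporting estimate and coaching-by-exercise as secondary.
3. **Rules.** State how the two endpoints are ordered or adjusted for multiplicity, and how visits without valid wear are handled.
4. **HIIT versus CME maintenance.** Use a companion model in all participants randomised at week 0, adjusted for baseline activity. The week-16 value is not suitable there, because it follows the first randomisation.
5. **Description.** Keep the three-category table as a supplement.

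In Sample Size Calculations, add the detectable difference for Aim 3, after reconciling the site table (actigraphy at UW/UCD only) with the Aim 3 Participants paragraph (up to 180).

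Cost: SAP wording, the main model for each endpoint and its companion, on accelerometry already planned. No extra participants are needed. Whether UAB actigraphy is already planned depends on that reconciliation; if it is not, the smaller number applies.

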will examine potential group (and site) differences in demographics and health and baseline measures with two-sample t test (or Wilcoxon), ANOVA (or Kruskal-Wallis test) or Chi-square test where appropriate. Variables that differ by group will be adjusted in sensitivity analyses. We will conduct primary analyses under an intention-to-treat principle (all participants analyzed based on randomized conditions). The impact of any missing data will be mitigated by the use of mixed effects modeling with baseline covariates that are conceptually relevant and associated to consistency in data collection. In the presence of missing data, mixed effects models are fitted with all available data and provide unbiased estimates of model parameters, as long as the data are missing at random or conditionally at random (conditional on the covariates). If appropriate, we will employ imputation techniques. False discovery rate (FDR) will be used to justify multiple comparison. All tests will be two sided.

Our primary aim is to determine the efficacy of HIIT vs CME on improving cognitive function over time. In stage 1 (baseline to 4 months), a general linear mixed model with participant ID as random effect:  $\text{score} = \text{Group} + \text{Time} + \text{Group} \times \text{Time} + \text{Site}$  will be used first to examine whether there is a significant group difference, wherein the study site is controlled to adjust for potential site effects. The best model fit with Bayesian information criterion (BIC) will determine the variance-covariance structure in above model. The significant interaction term in above model indicates a significant difference between two trajectories/slopes, i.e., treatment effect. The group comparison on the mean changes will also be contrasted with t test for effect size. In stage 2 (4 to 7 months), a similar general linear mixed model will applied:  $\text{score} = \text{Group1 (HIIT vs CME)} + \text{Group2 (Coaching vs Control)} + \text{Group1} \times \text{Group2} + \text{Time} + \text{Group1} \times \text{Time} + \text{Group2} \times \text{Time} + \text{Group1} \times \text{Group2} \times \text{Time} + \text{Site}$ , where the time is from 4 to 7 months. The non-significant interaction terms will be removed from the final model. Given any potential group differences in demographics and health at baseline, a sensitivity analysis will be conducted including those unbalanced variables in above models.

For exploratory analysis, sex-by-group interaction and/or race-by-group interaction will be included in above models to explore the potentially moderating effects, conducted according to the rigorous methods proposed by Hayes. Given significant treatment effects on cognitive function, a PATH analysis will be conducted to explore the potential mediation effects of biomarker changes on cognitive function. We will also examine whether changes in parent R01 outcomes (e.g., VO2, physical function, fatigue) mediate cognitive changes. The exploratory blood markers will be obtained at baseline, 4- and 12 months, while the MRI neuroimaging markers will be obtained at the UAB site at baseline and 4 months. The group difference of biomarkers will be evaluated using a similar linear mixed regression model:  $\text{scores} = \text{Group} + \text{Time} + \text{Group} \times \text{Time}$ , where the group difference on slopes and mean changes will be contrasted.

Our secondary aim is to examine psychological MoA of adherence to habitual PA at 12 months. We will examine distal predictors (i.e., sociodemographics, physical health, intervention type [HIIT vs CME and coaching vs control], changes in parent R01 outcomes [e.g., weight loss, physical function, fatigue] using laboratory and survey data, and proximal psychological predictors using EMA (e.g., self-efficacy, perceived benefits, motivation, social support). First, we will use a linear mixed regression with random intercept:  $\text{PA} = \text{Predictor} + \text{Time} + \text{Predictor} \times \text{Time} + \text{Site}$ , to examine the association between PA adherence and each of the predictors of interest, adjusting for study site. Secondly, we will conduct a multiple linear mixed regression with random intercept and all significant predictors detected above as fixed effects to examine the covariate-adjusted association between PA and predictors:  $\text{PA} = \text{Time} + \text{Predictor1} + \text{Predictor2} + \dots + \text{Site}$ . The time-by-predictor interactions will be evaluated and removed from the model if not significant. The variance-covariance structure (e.g., AR1) in above models will be determined by the best model fit measured by Bayesian information criterion (BIC).

For EMA data, a linear mixed regression model including random effects for subject and day (within-subject) to account for the multilevel structure of the data will be used to examine the time-lagged effects of MoA variables occurring during a specified time interval (T-1) on PA during the subsequent (lagged) time interval (T) within each day of monitoring:  $\text{PA}(T) = \text{MoA}(T-1) + \text{Time of Day} + \text{Day} + \text{site} + \text{covariates}$ . The time interval T can be time of day or different days, for example we can use the MoA in Day 1 to predict the PA in Day 2 or use the MoA in the morning to predict the PA later in the same day. The covariates include significant distal predictors. Moderating effects will be explored by including interaction terms in above model. Concurrent effects of these MoA variables on PA (i.e., both the predictor and outcome were assessed during the same time interval) will also be examined. To explore whether the MoA variables mediate intervention (HIIT vs CME and coaching texting vs control) effects on PA, mediation analyses with focus on effect estimation rather than hypothesis testing will be conducted using path analysis with methods considering the multi-level nature of data and robust to non-normality (e.g., cluster bootstrapping), assuming a causal chain of the form: Intervention (HIIT vs CME) --> effect on MoA [as mediator] --> effect on PA. Using the estimated path coefficients, direct, indirect, and total effects will be estimated and uncertainty on these estimates be estimated computed in the form of confidence intervals. Using similar mediation approaches, we will also examine whether cognitive differences between groups at 12 months are mediated by differences in PA adherence at 12 months.

Quantitative feasibility, acceptability, and intervention fidelity outcomes will be compared across sites and exercise type using analysis of variance or chi-square tests when applicable.

Qualitative analysis will be conducted for acceptability questions at 4 months and PA barriers and facilitators at 12 months. [name] and [name] have a history of designing and analyzing data from qualitative studies. Content analysis will be used to derive themes related to barriers and facilitators to long-term PA, which will be synthesized with quantitative data to examine correlates (e.g., demographics, health).

